9.4 Reporting Procedures for Serious Adverse Events

All SAEs (other than those defined in the protocol as not requiring reporting) must be reported on the SAE reporting form to R&D within 24 hours of the Site Study Team becoming aware of the event. The event will be recorded in the sponsor's SAE form (F44) and emailed to [contact] or faxed to the Joint R&D office ([name]) within the reporting timelines. R&D will perform an initial check of the report, request any additional information if required. Additional and further requested information (follow-up or corrections to the original case) will be detailed on a new SAE Report Form and faxed/emailed to R&D.

AEs (including SAEs) will be recorded from the Screening Visit to Month 12 visit. From Month 12-24 safety follow-up period, only SUSARs will be reported.

As stated in Section 5.1, DLTs will be assessed from Week 0 to Week 4 of the study.

9.4.1 Assessment of severity

- Mild: The subject is aware of the event or symptom, but the event or symptom is easily tolerated.
- Moderate: The subject experiences sufficient discomfort to interfere with or reduce his or her usual level of activity.
- Severe: Significant impairment of functioning; the subject is unable to carry out usual activities and / or the subject's life is at risk from the event.

9.4.2 Assessment of causality

- Probable: A causal relationship is clinically / biologically highly plausible and there is a plausible time sequence between onset of the AE and administration of the investigational medicinal product and there is a reasonable response on withdrawal.
- Possible: A causal relationship is clinically / biologically plausible and there is a plausible time sequence between onset of the AE and administration of the investigational medicinal product.
- Unlikely: A causal relation is improbable and another documented cause of the AE is most plausible.
- Unrelated: A causal relationship can be definitely excluded and another documented cause of the AE is most plausible.

9.4.3 Expectedness

Expectedness will be determined according to the Investigators' Brochure.

An adverse reaction, the nature, or severity of which is not consistent with the applicable product information (e.g. Investigator's Brochure for an unapproved investigational product or Summary of Product Characteristics (SmPC) for an authorised product).

When the outcome of the adverse reaction is not consistent with the applicable product information this adverse reaction should be considered as unexpected.

9.5 Reporting of Suspected Unexpected Serious Adverse Reactions (SUSARs)

All suspected adverse reactions related to an investigational medicinal product (the tested IMP and comparators) which occur in the concerned trial, and that are both unexpected and serious (SUSARs) are subject to expedited reporting.

9.5.1 Who should report and whom to report to?

The sponsor should report all the relevant safety information previously described to the concerned competent authorities and to the Ethics Committee concerned. The sponsor shall inform all investigators concerned of relevant information about SUSARs that could adversely affect the safety of subjects.

9.5.2 When to report?

Fatal or life-threatening SUSARs

The MHRA and the Research Ethics Committee should be notified as soon as possible but no later than 7 calendar days after the sponsor has first knowledge of the minimum criteria for expedited reporting.

In each case relevant follow-up information should be sought and a report completed as soon as possible. It should be communicated to the MHRA and the Ethics Committee within an additional eight calendar days.

Non-fatal and non-life threatening SUSARs

All other SUSARs and safety issues must be reported to the competent authority and the Ethics Committee in the concerned Member States as soon as possible but no later than 15 calendar days after the sponsor has first knowledge of the minimum criteria for expedited reporting. Further relevant follow-up information should be given as soon as possible.

Follow-up reports of SUSARs

In case of incomplete information at the time of initial reporting, all the appropriate information for an adequate analysis of causality should be actively sought from the reporter or other available sources. The sponsor should report further relevant information after receipt as follow-up reports. In certain cases, it may be appropriate to conduct follow-up of the long-term outcome of a particular reaction.

9.6 Development Safety Update Reports

The sponsor will submit (in addition to the expedited reporting above) a DSUR once a year throughout the clinical trial, or on request, to the Competent Authority (MHRA in the UK), Ethics Committee and the Host NHS Trust (if applicable).

9.7 Procedures used to assess participant safety

The research team will perform various clinical tests and procedures to assess participant safety during the whole duration of study. These include the following:

Medical history, Adverse Event review and Concomitant Medication review:

Systematic history will be taken from participant (and from the Parent/Guardian of the participant where necessary) to record any new and significant medical events and to review existing recorded medical history. Symptoms related to all body systems will be enquired about. Travel history, unwell contacts and allergy information will be recorded where appropriate. A complete listing of all concomitant medication received during the trial must be recorded in the relevant Concomitant Medication Log/electronic Case Report Form.

Remote review:

Telephone review conducted by a delegated study physician with full discussion with patients (and/or parents/guardians where appropriate) where any symptoms related to all body systems will be enquired about. As per the standard study review: medical history will be revisited and reviewed, An adverse events collection and concomitant medication review will be undertaken over the phone

and recorded in the relevant Adverse Event Log/Concomitant Medication Log/electronic Case Report Form. Travel history, unwell contacts and allergy information will be recorded where appropriate.

Physical examination:

Performed by a delegated study physician to include routine examination of the following systems:

- Respiratory system (including visual inspection of ear drum and throat).
- Cardiovascular system.
- Gastrointestinal system (including palpation for lymphadenopathy).
- Neurological system.
- Skin and wounds check.
- Height (cm), Weight (Kg) and Body Surface Area (recorded as per protocol requirements).

Vital signs checks:

Performed by an appropriate trained and delegated clinician to measure:

- Heart rate (beats/min).
- Respiratory rate (breaths/min).
- Oxygen saturations (%).
- Blood pressure (mmHg).
- Temperature (°C).

The normal values will depend on age of child and the following table can be referred to as a guide (Table 15) using the Advanced Paediatric Life Support Ranges [43]:

Table 15: Normal Vital Signs in Children:

Normal Vital Signs in Children (APLS Values)								
	Infant	1-2 years	2-5 years	5-12 years	Adolescent			
Pulse rate (bpm)	110-160	100-150	95-140	80-120	60-90			
Respiratory rate (rpm)	30-40	25-35	25-30	20-25	14-18			
Blood pressure Systolic mmHg	80-90	85-95	85-100	90-100	100-140			
Temperature (°C)	35-37	35-37	35-37	35-37	36-37.5			
Saturations (%)	94-98							

ECG:

Performed by an appropriate trained and delegated clinician to measure:

- Ventricular rate.
- Rhythm.
- QRS axis.
- QRS duration.
- Corrected QTC interval.

Comparison with previous ECG in medical records to occur where appropriate.

Transthoracic Echocardiogram:

Performed by an appropriate trained and delegated clinician to measure:

- Standard Transthoracic Echocardiogram views for cardiac structures and anastomoses sites from apical, parasternal long axis, parasternal short axis and suprasternal windows.
- Systolic functional assessment: Left Ventricular Ejection Fraction (LVEF) calculated by Simpson's biplane and on m-mode (Ejection Fraction by Teichholz formula).
- Right Ventricular function- comment on visual assessment and measurement of Tricuspid Annular Plane Systolic Excursion (TAPSE).
- Diastolic function parameters using tissue doppler interrogation: Mitral E wave and A wave velocities and ratio. Septal and lateral E/E' ratios and TVS' wave velocity.
- Any significant valvopathy on 2D echo and colour interrogation with doppler measurements (as required).
- The presence of pericardial effusion.
- Interval change(s) from previous tests.

Coronary vessel imaging:

The following imaging procedures are to be performed only in children above 25kg by an appropriate trained and delegated clinician:

- Coronary angiogram.
- Intravascular Ultrasound.

Blood tests:

The following tests are to be performed by an appropriate trained and delegated clinician:

- Clinical blood tests to assess: Haematology (full blood count), liver profile (albumin, alkaline phosphatase, total bilirubin and ALT levels), renal profile (sodium, potassium, creatinine and urea levels), LDH levels, EBV and CMV.
- Additional clinical blood tests to assess: bone profile, creatinine kinase (CK), CRP, ferritin, magnesium, uric acid levels and to coagulation screen.
- HLA antibody testing (includes panel reactive antibodies and donor specific antibodies)'
- Blood borne infection screen (with further details in Table 2 for the specific diseases and markers assessed).

Additional research blood tests will be collected at various study visits (as per Table 8) but will not be used for the safety assessment purposes.

Endomyocardial cardiac tissue biopsy:

Performed by a delegated study physician to as part of the routine post-transplantation examination.

10 Statistics

Since this study is assessing the toxicity of only two dose levels, adaptive designs for dose escalation based on statistical modelling which accelerate through lower doses were not deemed necessary.

10.1 Statistical methods to be employed (plan of analysis)

Biometric evaluation will be performed under the responsibility of [name]. Demographic data and baseline characteristics will be summarized to describe the populations analysed in this study (both all participants and participants administered each dose level). Efficacy parameters: clinical and immunological responses will be reported descriptively based on the per-protocol population. Time to first response will be summarized by Kaplan-Meier curve. Median time to event estimation as well as the associated 95% CI will be reported. All other secondary endpoints will be summarized by rates and corresponding 95% CIs.

All safety data will be analysed descriptively. Safety data will be reviewed between each patient cohort, with interim analyses provided to the DMC in order for decisions related to the next patient cohort to be made (decisions will be based on the 3+3 dose escalation design described in trial design section).

Statistical comparisons between patient populations are unlikely to be utilised, but if needed a 5% level of significance will be used.

A Statistical Analysis Plan will be written and will be signed off prior to database lock and will provide detailed information on all statistical analyses planned for the study.

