3.2 Objectives and endpoints

Objectives	Outcome Measures/Endpoints
Primary Objective: To determine safety and optimal tolerated dose of TR006 to prevent CAV in paediatric heart	Primary Endpoint: Occurrence and nature of Dose-Limiting Toxicities (DLTs) occurring within 4 weeks post-
transplant patients in a phase I study.	infusion of the expanded autologous thymus derived Treg product (ATIMP).
Secondary Objectives:	Secondary Endpoints:
1. To assess the feasibility of generating TR006 in the Good Manufacturing Practice facility.	Amount of TR006 manufactured per patient.
2. To investigate the clinical and immunological	Assessment of Immunological response:
responses to TR006 in paediatric heart	• Frequency of circulating leukocyte subsets.
transplant patients.	• Quantity of alloantigen-specific conventional T cells, Tregs and CD8+.
	 Presence of anti-HLA to evaluate tissue infiltrating cells.
	Assessment of clinical response:
	• Diagnosis of CAV as measured by coronary angiography within 24 months post-infusion of TR006.
	 Graft loss as measured by inclusion of patient on the re-transplant waiting list through rejection (acute or chronic) within
	24 months post-infusion of TR006.
	• Recipient mortality within 24 months post- infusion of TR006.
	 Acute graft rejection as measured by endomyocardial biopsy (EMB) within 24 months post-infusion of TR006.
	• Antibody-mediated rejection as measured by development of donor specific antibodies within 24 months post-infusion of TR006.

r	
	 Infection related rehospitalisation events within 24 months post-infusion of TR006.
	 (Cardiac function) Left ventricular ejection fraction as measured by echocardiography monthly for 12 months and at 24 months post-infusion of TR006.
	 (Renal function) Mean calculated GFR at 24months post-infusion of TR006.
	• Description of non-DLT adverse events and those occurring beyond week 4 and up to 24 months post-infusion of TR006.
	 Immunosuppressive doses at 12 and 24 months post-infusion of TR006.
3. To assess the feasibility of retaining participants for the duration of the study and completion of study visits and assessments	Number of study visits completed per participant.
	 Responses to items in questionnaires or surveys exploring the study and treatment experience of the participants and their parents/guardians.

4 Assessment and Management of Risk

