The diagram below (Figure 1) describes the decision-making process for proceeding with the next dosing cohort based on the DLTs experienced. If a DLT occurs in the Cohort 1, the next cohort of 3 patients will be administered to the same dose. If there is no DLT in Cohort 1, another cohort of 3 patients will be administered to next higher dose. From this study design, the trial will be stopped when 2 patients out of 6 receiving the same dose level experience a DLT. At this point, either a MTD will be identified (green endpoints in diagram) or the trial will be stopped for safety (red endpoints in Figure 1).

Based on this study design, a sample size of between 9 and 12 patients will be needed to identify the maximum tolerated dose. The 3+3 design requires that 6 patients are dosed at the selected dose level, this is often a requirement of adaptive design approaches as well (see Figure 1 below). These 6 patients dosed at the final selected dose level will provide useful information on haematological activity which will be expanded upon with the inclusion of additional patients.

Figure 1: DLT decision-making process

A DLT is defined as grade ≥ 2 CRS, grade ≥ 2 injection site reaction, grade ≥ 2 fever and/or rigors, grade ≥ 3 bronchospasm or grade ≥ 3 hypoxia occurring within the first 72 hours post infusion OR a grade ≥ 3 infection, moderate or severe acute rejection (as defined by the ISHLT criteria grade II-III), grade ≥ 3 haematological complication considered to be related to Treg infusion or any grade ≥ 3 toxicity not clearly related to underlying disease occurring within 4 weeks post TR006 infusion (see Section 5.1 for full definition). [38]

For the purposes of the primary endpoint regarding safety, any DLTs after the TR006 administration will be reported and compared.

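### Section 10.1 plans a Kaplan-Meier median for a response that no endpoint defines, and prescribes rates for secondary endpoints that are amounts or counts

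*Protocol*

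**What the plan says.** Protocol section 10.1 makes four statements about the secondary endpoints, in this order:

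- The clinical and immunological results are to be described without formal testing, in the per-protocol set.
- One time-to-event analysis is named: "Time to first response will be summarized by Kaplan-Meier curve".
- For that analysis, the plan promises an estimate of the median and its 95% CI.
- A single sentence then deals with whatever remains: "All other secondary endpoints will be summarized by rates and corresponding 95% CIs".

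The section closes by referring to a SAP that "will provide detailed information on all statistical analyses planned for the study".

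Section 3.2 lists the secondary endpoints. Apart from questionnaire answers, the word response appears there only in two group headings, one immunological and one clinical. The clinical group contains CAV, graft loss, death, acute rejection, antibody-mediated rejection, infection-related rehospitalisation, LVEF, renal function, adverse events and immunosuppressive doses. Renal function is specified as "Mean calculated GFR at 24months post-infusion of TR006". Outside those two groups are the amount of TR006 manufactured per patient, the number of visits completed per participant, and questionnaire responses.

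**The concern.** A Kaplan-Meier analysis needs an event, a time origin and a censoring rule. The protocol gives none of these for response, and no endpoint in section 3.2 supplies them. The trial aims to prevent CAV, so its clinical events are outcomes to be avoided, and a first response has no evident meaning among them.

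The sentence on rates is a separate mismatch. A rate with a confidence interval suits a binary event. It does not suit a cell yield, a visit count or an ejection fraction.

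The trial would then have three options: report a quantity it never defined, choose a definition with open-label data already in hand, or depart from its protocol. The manufacturing amount, which is the endpoint for the first secondary objective, would have no suitable summary.

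**Working it through.** **Inputs.** Nine participants, expandable to 12 (section 5.1): 3 cohorts x 3 = 9, and one further cohort of 3 gives 12. Both figures reproduce. The protocol gives no event rate for a response, so the risks below are assumptions, shown as a range.

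**1. Is there a response event?** Setting section 10.1 against section 3.2, there is none. The first part of the point rests on this comparison and needs no arithmetic.

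**2. If a listed harm was meant, would a median be reached?** With nine children and no censoring before the median, the Kaplan-Meier estimate is 5/9 = 0.556 after four events and 4/9 = 0.444 after five. At least five events are needed.

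For one anchor, section 1.1 gives 67% free of CAV at 10 years. Under an assumed constant hazard, the 24-month risk is 1 - 0.67^(24/120) = 0.077, or 9 x 0.077 = 0.69 expected events. The chance of a median is the upper binomial tail, P(X >= 5) for X ~ Bin(9, p):

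| Assumed 24-month risk p | P(at least 5 of 9) |
|---|---|
| 0.077 | 0.0003 |
| 0.30 | 0.0735 + 0.0210 + 0.0039 + 0.0004 = 0.099 |
| 0.50 | 0.50 (by symmetry) |

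**3. Could the interval for the median be given?** Assume every child has the event and use the order-statistic interval. Its widest form, minimum to maximum, has coverage 1 - 2 x 0.5^n:

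- n = 3: 75.0%, so no 95% interval exists.
- n = 6: 96.9%, which uses all six event times.
- n = 9: the 2nd to 8th ordered times give 1 - 2 x (1 + 9)/512 = 96.1%.

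A median with 95% CI by dose level is thus out of reach with three children and fragile with six, whatever the event.

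**4. Which endpoints does the rates sentence cover?** There are two readings of the word other.

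- *Narrow:* all endpoints except the clinical and immunological ones already reported descriptively. This leaves the TR006 amount (a quantity), visits completed (a count) and questionnaire items.
- *Broad:* all endpoints except time to first response. This adds LVEF, GFR, doses and cell frequencies, and contradicts section 3.2, which calls GFR a mean.

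The wording fails on both readings, for at least the TR006 amount and visits completed.

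**5. What would exact proportions show?** Clopper-Pearson 95% upper limits for zero events are 70.8% (n = 3), 45.9% (n = 6), 33.6% (n = 9) and 26.5% (n = 12). One event in nine gives 0.3% to 48.2%. These intervals are wide, but they can always be computed.

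**The case against.** The best defence is that section 10.1 is an outline and defers to a SAP. That is fair for censoring conventions, display and change from baseline. It does not cover the first part of the point: a SAP can add detail to a protocol endpoint, but here there is no endpoint to detail. It might also be said that rates can be derived, such as the share of products reaching the planned dose or of visits completed. Those would be different endpoints from the ones in section 3.2.

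Several stronger readings are tempting, and the documents do not support them.

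- **That the median is almost surely not estimable.** This holds only if response means CAV or a similar harm. The preceding sentence mentions immunological responses, which could be frequent. The accurate word is undefined. The 67% figure is also for all ages, section 1.1 warns that angiography may understate disease, and only children over 25 kg are imaged, so nine is not the CAV denominator.
- **That every continuous endpoint is to be reported as a rate.** On the narrow reading, LVEF, GFR, doses and cell frequencies are already reported descriptively.
- **That the plan ignores pre-dose values.** Section 2.1 plans alloreactivity assays before and after infusion, section 7.7(c) does the same for biopsies, and section 9.7 records interval change on echocardiography.
- **That change from baseline must gain precision.** The half-width of the interval changes by a factor sqrt(2(1 - r)). From 0.77 SD at n = 9, it becomes 0.60 SD at r = 0.7, stays at 0.77 SD at r = 0.5, and widens to 0.91 SD at r = 0.3. The protocol gives no correlation.
- **That the SAP comes too late.** A SAP that "will be signed off prior to database lock" is conventional, and the 3+3 decisions rest on rules in the protocol itself.
- **That the phrase "useful information on haematological activity" in section 10.2 is a further undefined endpoint.** It is a background remark, and no planned analysis uses it.

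**Conclusion.** The point holds in two parts. First, the Kaplan-Meier curve and median for time to first response have no defined event and cannot be run as written; this needs no assumption. If a listed harm was intended, the chance of reaching a median among nine children is about 10% at an assumed 30% risk, and 0.0003 at the 7.7% implied by the protocol's CAV figure under constant hazard. Both figures assume no earlier censoring. Second, rates are the wrong summary for at least the TR006 amount and visits completed and, on the broader reading, for LVEF, GFR, doses and cell frequencies.

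The consequence is limited to secondary descriptive reporting. The DLT primary endpoint and the escalation rule do not depend on either sentence.

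**What to change.** In section 10.1:

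1. Delete time to first response and its median.
2. Report rejection, CAV, graft loss and death as proportions with exact (Clopper-Pearson) 95% CIs over the 24-month follow-up, using only imaged children as the denominator for CAV. State that the scheduled post-infusion biopsy is at Month 3 and the scheduled post-infusion angiography at Month 9, in children over 25 kg only (section 7.5 and Appendix B). Findings at other times would come from unscheduled procedures.
3. Replace rates for continuous and count endpoints with mean or median, spread and individual profiles. Group by dose received, because section 8.5 allows a participant to receive less than the planned dose.
4. For LVEF and GFR, show the pre-infusion value and the within-participant change beside the post-infusion value. Echocardiography, renal bloods and height are already collected on Baseline Day 0 (section 7.4), and this matches the before/after use in sections 2.1 and 7.7(c).
5. Show immunosuppressive doses against the pre-infusion dose, each drug in its own dosing unit (mycophenolate is given per m2 in Table 9). Note that routine tapering contributes to any change, since the tabulated tacrolimus targets vary with time since transplant.

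The cost is protocol wording, carried through to the SAP. No new visit, procedure or data item is needed.
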